21.0 Provisions to Monitor the Data to Ensure the Safety of Subjects

Safety monitoring is required when research involves greater than minimal risk and is sometimes appropriate for other studies.

21.1 Describe:

- *The plan to periodically evaluate the data collected regarding both harms and benefits to determine whether subjects remain safe (e.g., periodic reporting to the IRB, establishing a data monitoring committee, reporting data monitoring committee findings to the IRB and the sponsor).*
- *What data you will review, including safety data, unexpected events, and data that show the ability to produce the intended results.*
- *How the safety information will be collected (e.g., with case report forms, at study visits, by telephone calls with subjects).*
- *The frequency of data collection, including when safety data collection starts.*
- *Who will review the safety data and with what frequency.*
- *The statistical tests for analyzing the safety data to determine whether harm is occurring.*
- *Any conditions that will trigger an immediate suspension of the research (e.g., a serious adverse event).*

The data safety monitoring plan (DSMP) for this study focuses on close monitoring by the principal investigator (PI) and research staff along with prompt reporting of excessive adverse events and any serious adverse events (AEs) to the Institutional Review Board. All serious AEs will be reported by the PI within 48 hours of occurrence to the IRB and the sponsor.

The safety data monitored will include data related to the blood collections, fitness testing and the supervised exercise sessions. Specific safety data include any reports of pain, excess swelling, redness or bruising after the blood draws at the needle insertion site, feelings of light headedness, chest tightness or pain or fatigue on exertion during exercise testing procedures, and symptoms of muscle soreness, joint pain, or unexpected events/issues during the 5 days of consecutive running and 5 days of consecutive running with impact loading exercises. Data will be collected and documented in the participant's chart if a situation arises or when observed by a member of the research team or reported by a participant during a study visits or during supervised resistance training sessions using a general TBD incident reporting form. Safety data will also include excessive changes in body weight or interstitial glucose concentration that will measured throughout the 5 days of energy restriction in the experimental conditions.

The graduate student in charge of the project ([name]) will consult with Drs. [name] and [name] and be responsible for assembling the data, producing reports, and assuring that all parties obtain copies of these reports. Reports will be submitted annually to the VT IRB for review.

Safety Data collection will start when the first participant is screened and enrolled. The study team will be informed to discuss any observed or reported unusual, excessive or unexpected events immediately with the PI. The PI and/or authorized study personnel

22-168 The Effect of Impact Loading on Bone Biomarkers in Energy-Restricted Female Runners

will review study charts and ongoing data collected on all participants on a weekly basis to ensure safety. In our small study, it is unlikely that use of statistics would be necessary to determine if excessive events were occurring; however, paired t-tests could be used if appropriate. We do not anticipate that there would be any specific events, other than the unexpected, that would trigger the suspension of our study.

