4.0 Study Endpoints

4.1 *Describe the primary and secondary **study** endpoints. See links below for discussion of study endpoints and how they may differ from study objectives. These are most common in clinical trials but are sometimes applicable to other types of biomedical research, as well as social, behavioral, or educational research. See link below for a discussion.*

https://docs.google.com/document/d/1Wocz7K7a0hCQJPPO_khh5l1SQQjhGDDGHzcOPRHR5Tw/edit?usp=sharing

Primary Endpoints

Change in Biomarkers of Bone Remodeling in Blood including N-terminal propeptide of type 1 procollagen, undercarboxylated osteocalcin, sclerostin, and C-terminal telopeptide of type 1 collagen.

22-168 The Effect of Impact Loading on Bone Biomarkers in Energy-Restricted Female Runners

Change in Hormone and Metabolic Markers in Blood including parathyroid hormone, estrogen, insulin-like growth factor 1, hepcidin, insulin, cortisol, leptin, Nesfatin-1, and thyroid hormones

24-h Glucose

Secondary Endpoints

Change in Running Economy

Change in Body Weight

Change in ferritin, TIBC, iron, vitamin D

4.2 *Describe any primary or secondary safety endpoints. These should be included for all studies that are greater than minimal risk. (Minimal risk: The probability and magnitude of harm or discomfort anticipated in the research that are not greater in and of themselves than those ordinarily encountered in daily life or during the performance of routine physical or psychological examinations or tests.):*

Safety Endpoints

Excess weight loss (>5 lbs. during the 5-day experimental conditions)

Excessive change in absolute value for 24-hour glucose concentration

Excessive muscle soreness and/or pain

Fainting or light-headedness

Muscle or joint injury

General fatigue

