protocol in section 8.1) to elicit an EEE of 15 kcal/kgFFM. In the RUN+IL condition, participants will perform impact loading movements (jumping) and a running protocol. Participants will come to the lab in the morning to perform 5 sets of 10 impact loading movements for a total of 50 impacts/session at intensities greater than 2x bodyweight. Each jumping set will be separated by 60 seconds of rest in alignment with guidelines for osteoporosis prevention recommended by the Exercise and Sport Science Australia (ESSA) (Beck, Daly et al. 2017). Ground reaction force of impacts will be measured using dual force plates. Approximately 4-6 hours later, participants will return to the lab to complete a 5-min run and warm-up on the treadmill at 65% VO₂max until a combined energy expenditure of the morning impact loading exercise and afternoon/evening treadmill running reaches 15 kcal/kgFFM. A recovery period of at least 4 hours is recommended between impact loading sessions for optimal osteogenic bone response (Hart, Nimphius et al. 2017). Participants will wear accelerometers and smart watch devices during the experimental conditions to measure activity level. Participants will be instructed to refrain from all physical activity outside of the supervised exercise sessions that are not related to activities of daily living (e.g., getting dressed, walking to the car).

Body Weight: Body weight will be obtained before each supervised exercise session begins using a digital physician's scale to monitor significant changes in body weight during the intervention. Participant body weight will also be needed for monitoring the impact of the jumping exercises using ground reaction force in the RUN+IL condition. The scale and monitor will be separate and daily body weight will not be shared with participant.

Ground Reaction Force (GRF): Ground reaction force of jumping exercises will be performed using dual force plates. Participants will perform 5 sets of 10 vertical jumps with 60 seconds of rest between each set. Jumping exercises will be tailored until intensity reaches a threshold of at least 2x body weight of participant. These jumping exercises will be used in the RUN+IL condition.

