Energy Restriction: Potential risks associated with energy restriction include loss of lean body mass (LBM), suboptimal macronutrient and micronutrient intake, hypoglycemia, and mood disturbances. These risks will be minimized by providing a daily multivitamin to participants for the duration of the 5-days of energy restriction. Menus will also be designed to provide 20% of total calories from protein to help preserve LBM. To reduce risk of hypoglycemia, diets will provide 55% of total calories from carbohydrates and participants will be encouraged to consume the provide snack containing 30g carbohydrate approximately 30 minutes before the exercise sessions. Additionally, menus will be designed to prioritize foods with fiber and low energy density that promote fullness and satiety (e.g., leafy greens, fresh non-starchy vegetables, whole grains and other high-fiber foods) to reduce physical and psychological burden of energy restriction. Participants with existing menstrual disturbances (determined by progesterone and self-report), LEA (determined by LEAF-Q score), and/or low BMD (determined by DXA) will be excluded from the study to prevent worsening existing conditions.

High-Intensity Exercise: Potential risks associated with endurance running and high-impact loading exercises include musculoskeletal injuries, changes in blood pressure, gastrointestinal discomfort, fainting, and dizziness. These risks will be minimized by

22-168 The Effect of Impact Loading on Bone Biomarkers in Energy-Restricted Female Runners

having participants assessed prior to each exercise session by a trained research member to evaluate readiness for physical activity. Additionally, participants will complete all exercise sessions in the lab under the supervision of a certified strength and conditioning specialist with CPR certification ([name]).

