CGM: Potential risks associated with the CGM include discomfort during the insertion, pain, inflammation, redness/rash, swelling, minor bleeding and minor infection at the site. These risks will be minimized by having a trained member of the research staff perform the procedure under aseptic conditions. Participants might also experience the aforementioned symptoms as a result of contact between the adhesive pad of the sensor and the skin. In rare cases, an infection can spread to other parts of the body. Allergic reactions can develop in response to the adhesive used to keep the CGM in place. If these symptoms occur, participants have the ability to remove the CGM at will. Symptoms typically resolve within a short time (approximately one week).

Questionnaires and Study Logs: All study questionnaires (except the food records) will be collected with the participant sitting in a private setting in the laboratory. Questionnaires will be placed in each participant's study file date entered for data analysis.

Blood draws: Blood will be collected using universal precautions by a trained technician. Blood will be drawn by venipuncture from a vein in the arm with the participant resting in a phlebotomy chair. Blood will be drawn at five times during the study (baseline, RUN day 1, RUN day 7, RUN+IL day 1, RUN+IL day 7) with a total of 110 ml of blood collected over the course of the 5-6 weeks.

DXA scan: Participants will be exposed to a very low dose of ionizing radiation as part of the DXA scan at baseline only. DXA procedure will be performed by trained staff. Participants will be informed of the risk of radiation exposure prior to study enrollment. Female participants will complete a pregnancy test by urine immediately before the DXA.

VO2max/Aerobic capacity: Trained research personnel will be present during the test to correctly place the mouthpiece, monitor all variables during the test and support the participant at the end of the test.

8.4 What data will you collect during the study and how you will obtain them? Please include descriptions of electronic data collection, database matching, and app-based data collection:

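### Four of the six safety endpoints have no scheduled question and no defined end of collection, and under Section 8.2 RUN+IL gives more occasions to chart them than RUN

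*Combined protocol and SAP*

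**What the plan says.** Section 4.2 lists six safety endpoints. Excess weight loss has a threshold (more than 5 lbs within a condition). The symptom endpoints, such as "Excessive muscle soreness and/or pain", have no scale, threshold or time point.

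Section 21.1 treats the two groups differently. For weight and glucose: "Safety data will also include excessive changes in body weight or interstitial glucose concentration that will measured throughout the 5 days". Section 8.2 supports this, with weighing before every supervised session and a glucose sensor worn over the same days in both conditions. For symptoms: "Data will be collected and documented in the participant's chart if a situation arises or when observed by a member of the research team", or on a participant's report, "using a general TBD incident reporting form". Section 21.1 places soreness and joint pain within the five exercise days of each condition, and light-headedness and exertional fatigue within exercise testing. It says when safety collection starts but not when it ends.

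For RUN+IL, Section 8.2 has a morning jump session and then: "Approximately 4-6 hours later, participants will return to the lab". Section 8.1 describes the jumps followed by the run, with no return visit.

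Three other provisions bear on the point:
- Section 8.3 plans on "having participants assessed prior to each exercise session by a trained research member to evaluate readiness for physical activity".
- Section 17.1, in its paragraph on jumping, tells participants to contact the team about injury or strain.
- Section 21.1 provides for weekly chart review.

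**The concern.** Symptoms that are written down only when noticed or volunteered depend on how often someone is there to notice. If one condition brings a woman to the laboratory more often, it can show more recorded symptoms with no difference in true harm.

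The collection window is also short compared with what the plan expects. Section 17.1 allows for sore muscles for a few days after exercise testing and names excessive bone strain as a risk of jumping. Section 8.3 says of the glucose sensor site: "Symptoms typically resolve within a short time (approximately one week"). The sensor comes off on the day after each condition. Sensor-site reactions and mood disturbance are named as risks in Sections 8.3 and 17.1 but do not appear among the specific safety data in Section 21.1.

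Section 3.3 presents jumping as a practical countermeasure for runners with low energy availability and foresees longer trials, so readers will use what this study reports on tolerability. With at most 20 women, a few unevenly recorded events could change that impression.

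**Working it through.** **1. Is any study day planned after the last Day 7?** Section 1.0 gives 19 days. One screening visit + one baseline visit + 3 tracking days + 2 × 7 condition days = 19. The figure reproduces and leaves no day over. Section 15.4 says the washout needs no laboratory visits, and Section 8.7 answers the follow-up question as not applicable. Payment after each condition (Section 15.4) and the offer of individual results (Section 10.1) are contacts, but neither is linked to safety data.

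**2. Which endpoints are scheduled?** Weight and glucose: 2 of 6. The other four depend on report or observation.

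**3. Attendances per condition.**

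| Reading | RUN | RUN+IL | Ratio |
|---|---|---|---|
| Section 8.2, exercise attendances on Days 2-6 | 5 × 1 = 5 | 5 × 2 = 10 | 2.0 |
| Section 8.2, plus Days 1 and 7 | 7 | 12 | 1.71 |
| Section 8.1, exercise attendances | 5 | 5 | 1.0 |
| Section 8.1, plus Days 1 and 7 | 7 | 7 | 1.0 |

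Calendar days are 7 in both conditions on either reading.

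**4. Illustration of the capture imbalance under Section 8.2.** Suppose a symptom is equally present in both conditions throughout Days 2-6, and each exercise session independently leads to a chart entry with probability p. Then P(charted at least once) = 1 − (1 − p)^k, with k = 5 for RUN and k = 10 for RUN+IL. The documents give no value for p, so these values are assumed.

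| p | RUN (k = 5) | RUN+IL (k = 10) | Ratio |
|---|---|---|---|
| 0.05 | 22.6% | 40.1% | 1.77 |
| 0.10 | 41.0% | 65.1% | 1.59 |
| 0.20 | 67.2% | 89.3% | 1.33 |
| 0.50 | 96.9% | 99.9% | 1.03 |

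The ratio cannot exceed 2 under this formula. At p = 0.02 it is 1.90 (9.6% against 18.3%). Counting all attendances (k = 7 and 12), it runs from 1.52 at p = 0.05 to 1.01 at p = 0.50.

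Duration matters too. At p = 0.3:
- a one-day symptom gives 30% against 51% (1.70);
- a three-day symptom gives 65.7% against 88.2% (1.34);
- a five-day symptom gives 83.2% against 97.2% (1.17).

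**5. Time after the last jumps.** Jumps end on Day 6. If RUN+IL comes second, the last visit is the next day. If it comes first, the next Day 1 follows about 3 weeks later, but nothing says which condition an event surfacing then belongs to. The same holds for RUN with the order reversed.

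**The case against.** The plan has more safety monitoring than Section 21.1 alone suggests: a staff assessment before every session, supervision of all sessions, an instruction to contact the team, and weekly chart review. This stands as protection for the individual woman. It does not make recording uniform. The readiness assessment is not tied to the Section 4.2 symptoms, chart review sees only what was charted, and the contact instruction appears only in the jumping paragraph.

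Section 8.1 gives no doubling of sessions. That also stands. The excess exists only under Section 8.2. The revision history records a recovery period being added to the impact sessions there, but this does not settle which text governs.

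No objective or hypothesis compares harms, and Section 5.2 has no safety analysis. Section 21.1 thinks statistics unlikely to be needed, though it allows paired t-tests. This limits the consequence to how tolerability is described; the primary results are not affected.

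A reader might infer three stronger things that the documents do not support:
- **That harms in general are recorded only by chance.** Weight and glucose are scheduled in both conditions.
- **That collection stops on the final Day 7.** No end is stated, and the contact instruction has no time limit. Only the absence of a later scheduled safety contact is shown.
- **That the short follow-up after the second condition biases the comparison against or in favour of jumping.** Order is randomised and RUN has the same short follow-up when it comes second, so late events are lost without this by itself favouring one condition.

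**Conclusion.** The point holds for four of the six safety endpoints. Symptom recording is unscheduled, and under Section 8.2 RUN+IL gives 10 exercise attendances against 5, or 12 against 7 overall. The likely direction is more charted symptoms in RUN+IL for equal true harm. The size is unknown. The range of about 1.0 to 1.8 rests on an assumed p of 0.50 to 0.05, independence between sessions, and a symptom lasting all five exercise days. It is negligible if reporting is near complete, and there is no imbalance from session count if Section 8.1 describes what is done.

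Separately, late symptoms can be missed in either condition, because soreness and joint pain are tied to the exercise days and no safety contact follows the last Day 7. The change is worth making because it is cheap and builds on a check already planned.

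**What to change.** 1. **Use one matched question.** Turn the readiness check in Section 8.3 into a short fixed checklist covering the Section 4.2 symptoms, the sensor site and mood. Ask it once a day, at the first attendance on Days 2-6 and on Day 7, in both conditions. That is 5 + 1 = 6 askings each, a ratio of 1.0 whichever session layout applies. Use these answers for any between-condition symptom comparison.
2. **Keep everything else.** Report all events during or between sessions, including during jumping, separately and in full. Restricting the record to answers given just before the treadmill run would drop events during the jumps, and would miss a woman hurt by jumping who does not reach the run that day.
3. **Define the window in Section 21.1.** Extend soreness and injury collection beyond the five exercise days. Schedule one call or message about a week after Day 7 of each condition and state it as the end of active collection. Attribute events reported before the next Day 1 to the preceding condition. The week is the plan's own figure for sensor-site symptoms. The documents give no such figure for bone strain, so later reports should still be accepted.
4. **Reconcile Sections 8.1 and 8.2** on whether RUN+IL is one attendance or two per day.

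The cost is one checklist page and two brief messages per woman, which can be attached to the payment or results contact, with no new visit. The downside is that direct questions will record more mild symptoms, in both conditions.

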22.0 Compensation for Research Related Injury

22.1 If the research involves more than minimal risk to subjects, describe the available compensation in the event of research-related injury, if any:

Participants will not be provided any form of compensation for medical treatment or other damages (for example lost wages, time lost from work, etc.). If a participant becomes injured or sick from the research, they will be referred to a clinic or to their personal health care provider. Medical treatment may be provided at their expense or at the expense of their insurance company.

22.2 Provide a copy of contract language, if any, relevant to compensation for research-related injury. At Virginia Tech, this is most common for sponsored research:

N/A

23.0 Economic Burden to Subjects

23.1 Describe any costs that subjects might be responsible for because of participation in the research, including any uncompensated costs for items such as transportation, missed work, and childcare:

The participant will be responsible for costs that may include purchase of athletic clothes or shoes to participate in the running and impact loading exercise sessions or the uncompensated cost that might include transportation, missed work, or childcare.

24.0 Consent Process

24.1 Indicate the process by which you will obtain consent for study participation. Please upload all consent, parental permission, and assent forms, documents, and scripts referenced in this section to Protocol Management.

Describe the following:

- *Where the consent process will take place (e.g., clinic waiting area, classroom, online)*
- *The time interval between sharing the consent information with the prospective subject and obtaining consent. For lab, interview, and focus group studies, the Virginia Tech IRB prefers that subjects have at least 24 hours to review the consent form and study information before the appointment where consent will be obtained. For simple online survey studies, you can typically present the consent information immediately before subjects begin participation.*
- *If applicable, processes to ensure ongoing consent or assent (e.g., for multiple sessions; for research in which a minor will turn 18 during the study; for longitudinal research with minors who will later be asked to provide or affirm their assent).*
- *Please review “SOP: Informed Consent Process for Research (HRP-090)” for recommended procedure. Describe your process, being sure to include:*
 - *The name and role of all study personnel who will be trained and certified by the PI to conduct the consent process*
 - *The time that will be devoted to the consent discussion*
 - *Steps that you will take to minimize the possibility of coercion or undue influence*
 - *Steps that you will take to gauge or ensure the subjects’ understanding*

Participants will be first screened over the phone (phone script and screening form uploaded). The phone screening will include an overview of the study, the time commitment and the possible risks to participation. After explaining the study and before conducting the phone screen, a study team member will describe the purpose of the phone screen and what type of data will be collected, and then ask that the participant provide verbal permission to conduct the phone screening. They will also be informed that they may refuse to answer any and all questions. An informed consent form will be emailed (or mailed) to the participant following the phone screening and at least 24 hours in advance of coming to the laboratory for the screening visit (email template uploaded).

At the start of the screening visit, a team member will provide potential participants with a written copy of the study consent form and review the document with the participant. Participants will be encouraged to ask questions and seek clarification during the phone screening. The

participant will then be encouraged to ask questions before providing written consent. As much time as necessary will be devoted to address participant concerns. Once the participant is ready to sign, she will be allowed to sign in a private room near the door where they may also exit the lab if they no longer wish to participate. Screening and informed consent will be performed by the doctoral student in charge of the study ([name]). Participants will be encouraged to ask questions and seek clarification during the phone screening and before signing the consent at the beginning of the laboratory screening visit.

These steps including time to review the consent before the screening visit, time with study staff to review the protocol and address concerns, and time to sign the consent in a private setting and close to a laboratory exit will help minimize the possibility of coercion or undue influence.

To help gauge the participant's understanding, the team member will ask the participant to explain the study, when they need to notify the team about the start of menstruation, how often they will be asked to consume the meals and snacks provided by the research team, what foods and beverages they can consume outside of the ones provided by the research team, what physical activities they can do outside of the ones conducted in the NEM lab, and how often they would need to come to the lab to run.

Non-English Speaking Subjects

- *Indicate what language(s) other than English are understood by prospective subjects or representatives.*
- *If non-English speakers will be recruited, describe the process you will use to ensure that the oral and/or written consent information provided will be in a language that they understand.*
- *If you translate consent forms and study materials, please provide a certified translation of the form as well as the certification document.*
- *Indicate the spoken language that study personnel obtaining consent will use. Describe how you will assess fluency of personnel obtaining consent to ensure that the translation is accurate.*

Only English-speaking participants will be recruited for the study.

Waiver or Alteration of Consent Process (consent will not be obtained, required information will not be disclosed, or the research involves deception)

- *Review the “CHECKLIST: Waiver or Alteration of Consent Process (HRP-410)” to ensure you have provided sufficient information for the IRB to make these determinations (i.e., that it meets the criteria for a waiver or alteration of the consent process).*

N/A

Subjects who are not yet adults (minors: infants, children, teenagers)

- *Describe the criteria that you will use to determine legal age for consent to treatments or procedures involved in the research under the applicable law of the jurisdiction in which the research will be conducted (e.g., in Virginia, individuals under the age of 18 years).*
 - *For research conducted in Virginia, review “SOP: Legally Authorized Representatives, Minors, and Guardians (HRP-013)” to determine which individuals in the state meet the definition of “minor.”*
 - *For research conducted outside of the state, please describe the legal requirements for the definition of “minor.”*
- *Describe the process for obtaining parental permission.*
 - *Permission from one parent is acceptable for studies that involve no greater than minimal risk OR involve greater than minimal risk but present the prospect of direct benefit to the minor subject.*
 - *Permission from both parents is required in all other cases (unless one parent is deceased, unknown, incompetent, or not reasonably available, or when only one parent has legal responsibility for the care and custody of the minor).*
- *Describe whether you will obtain permission from individuals other than parents or Legally Authorized Representatives, and if so, who will be allowed to provide permission. Describe the process you will use to determine these individuals’ authority to consent to the minor’s general medical care.*
- *Indicate whether you will obtain assent from all, some, or none of the minors. If you will obtain assent from some minors, indicate which minors will be required to assent. Consider chronological age and intellectual capacity when determining who will be required to provide assent (e.g., infants are unable to assent. However, teenagers are likely able to read and sign an assent form).*
- *When assent of minors is obtained, describe whether and how you will document it. Will minors sign an assent form or give verbal assent?*
- *Attach parental permission and minor assent forms or scripts in Protocol Management.*

N/A

Adults Unable to Consent

- *Describe the process you will use to determine whether an individual adult is capable of consent.*
- *List the individuals from whom you will obtain permission in order of priority (e.g., durable power of attorney for health care, court appointed guardian for health care decisions, spouse, and non-minor child).*
 - *For research conducted in the Virginia, review “SOP: Legally Authorized Representatives, Minors, and Guardians (HRP-013)” to determine which individuals in the state meet the definition of “legally authorized representative.”*
 - *For research conducted outside of Virginia, please describe the legal requirements for obtaining permission from a legally authorized representative in the state where the research will occur.*
- *Describe the process for assent of the subjects.*
 - *Indicate whether you will require assent from all, some, or none of the subjects. If some, indicate which subjects will be required to assent and which will not.*
 - *If you will not obtain assent from some or all subjects, please provide justification for not obtaining assent.*
 - *Describe whether and how you will document assent.*

N/A

